5.6.1. Extent of Exposure

The number and percentage of participants who receive study intervention will be summarized.

Descriptive statistics for duration of study intervention (N, mean, SD, median, range, minimum, maximum) will be summarized.

Duration of intervention during the double-blind phase will be summarized in the following duration categories: <2 week, 2-<4 weeks, 4-<6 weeks...10-<12 weeks for each study agent within a study intervention and presented graphically in a histogram. Cumulative duration of intervention [>=2 week, >=4 weeks, ...] will also be summarized. Frequency distribution of duration of intervention during the open-label phase (week 1-4, week 5-8,...,week 101-104, or >week 104) will also be summarized.

Total duration of intervention for the double-blind phase and open-label phase is defined as (date of last dose of study intervention – date of first dose of study intervention) +1. If the date of last dose of study intervention is missing, it will be imputed as the day prior to the double-blind or

open-label disposition date for calculating exposure duration. Descriptive statistics (N, mean, SD, median, range, minimum, maximum) of total duration of intervention will be summarized for each study drug within a study intervention.

Total dose days of intervention is defined as the total number of days that study intervention was administered to the participant (excluding days off study intervention). Descriptive statistics (N, mean, SD, median, range, minimum, maximum) of total dose days of intervention will be summarized for the double-blind phase and open-label phase for each study agent within a study intervention.

A listing to show all dose adjustments for each participant including the reason for dose adjustment will be provided.

Study intervention compliance during DB and OLE will be summarized descriptively. See Appendix 7 for further details.

The analysis will be performed on SAF and SAFOLE analysis sets.

5.6.2. Adverse Events

The verbatim terms used in the CRF by investigators to identify adverse events will be coded using the Medical Dictionary for Regulatory Activities (MedDRA). Any AE occurring at or after the initial administration of study intervention through the day of last dose plus 5 days is considered to be treatment emergent. If the event occurs on the day of the initial administration of study intervention, and either event time or time of administration are missing, then the event will be assumed to be treatment emergent. If the event date is recorded as partial or completely missing, then the event will be considered to be treatment emergent unless it is known to be prior to the first administration of study intervention based on partial onset date or resolution date. All reported treatment-emergent adverse events will be included in the analysis. For each adverse event, the number and percentage of participants who experience at least 1 occurrence of the given event will be summarized by intervention group.

Assignment of adverse events to double-blind or open-label analysis phase, or the follow-up phase will be made based on the following rules:

Double-blind analysis phase:

All AEs that are assigned to the double-blind analysis phase as detailed below will be considered as treatment-emergent.

• For participants who did not continue to open-label treatment phase: double-blind phase start date ≤ AE onset date ≤ date of the last dose of study intervention in the double-blind phase plus 5 days.

- For participants who continued to open-label treatment phase: double-blind phase start date ≤ AE onset date ≤ earlier of (date of the last dose of study intervention in the double-blind phase + 5, open-label study intervention start date)
 - AEs that occur more than 5 days after the last dose of double-blind study intervention but prior to open-label dosing will not be considered as treatmentemergent for either the double-blind or the open-label phase. These AEs will be flagged as 'Pre-open label';

Open-label analysis phase:

All AEs that are assigned to the open-label analysis phase as detailed below will be considered as treatment-emergent.

- For participants who entered open-label treatment phase < 6 days from the last dose doubleblind study intervention: open-label phase start date < AE onset date ≤ date of the last dose of study intervention in the open-label phase plus 5 days.
- For participants who entered open-label treatment phase ≥ 6 days from last dose of double-blind study intervention: open-label phase start date \leq AE onset date \leq date of the last dose of study intervention in the open-label phase plus 5 days.

Follow-up phase:

AEs that are assigned to the follow-up phase are not considered as treatment-emergent. AEs with onset date > date of last dose of double-blind study intervention plus 5 days will be assigned to this phase.

Summary tables will be provided for treatment-emergent adverse events:

- AEs
- Serious AEs (SAEs)
- AEs leading to discontinuation of each study drug within a study intervention/termination of study participation
- AEs by relationship to study intervention
- AEs leading to dose interruption of each study agent within a study intervention.

In addition to the summary tables, listings will be provided for participants who:

- Had SAEs
- Had AEs leading to discontinuation of study intervention/termination of study participation A listing of participants who died will be provided.

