# 2.2.3. Brivaracetam

Brivaracetam is an antiepileptic drug indicated as adjunctive therapy in the treatment of partial-onset seizures in patients 16 years of age and older with epilepsy.

Brivaracetam displays a high and selective affinity for synaptic vesicle protein 2A (SV2A), a transmembrane glycoprotein found at presynaptic level in neurons and in endocrine cells. Although the exact role of this protein remains to be elucidated it has been shown to modulate exocytosis of neurotransmitters. Binding to SV2A is believed to be the primary mechanism for brivaracetam anticonvulsant activity.

The recommended starting dose in adults is either 50 mg/day or 100 mg/day based on physician's assessment of required seizure reduction versus potential side effects. Based on individual patient response and tolerability, the dose may be adjusted in the effective dose range of 50 mg/day to 200 mg/day.

The following adverse reactions have been reported as the most common. For details see the Summary of product characteristics for brivaracetam.

- Very common: may affect more than 1 in 10 people somnolence dizziness
- Common: may affect up to 1 in 10 people influenza depression, anxiety, insomnia, irritability decreased appetite convulsion, vertigo upper respiratory tract infections, cough nausea, vomiting, constipation fatigue

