#### **Adverse Events**

The verbatim terms used in the eCRF by investigators to identify AEs will be coded using the MedDRA. All reported AEs with onset during the double-blind treatment period (i.e., TEAEs, and AEs that have worsened since baseline [Day 1]) will be included in the analysis. For each AE, the percentage of participants who experience at least one occurrence of the given event will be summarized by treatment group. Summaries will be provided for all participants receiving at least one dose of study intervention in this study and will include AEs from this study.

Summaries, listings, datasets, or participant narratives may be provided, as appropriate, for those participants who die, who withdraw due to an AE, or who experience a severe AE or a SAE.

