6.2. Appendix 2 Changes to Protocol-Planned Analyses

There have been no changes to protocol-planned analyses.

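### SAP 5.6.2 classifies AEs as treatment-emergent by onset date only, so an AE first recorded before dosing that worsens on treatment on the same record drops out of the AE summary tables

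*SAP*

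**What the plan says.** SAP 5.6.2 defines as treatment-emergent "Any AE occurring at or after the initial administration of study intervention through the day of last dose plus 5 days". It then sorts AEs into phases. For the double-blind phase the test begins "double-blind phase start date ≤ AE onset date", with an upper limit of last double-blind dose plus 5 days (or open-label start, if earlier). The open-label rules have the same form. An event with a partial or missing date counts as treatment-emergent "unless it is known to be prior to the first administration of study intervention based on partial onset date or resolution date". None of these rules mentions a change in severity or seriousness.

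On outputs, the section states: "Summary tables will be provided for treatment-emergent adverse events". The only AE listings it adds cover SAEs, AEs leading to discontinuation or termination, and deaths.

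Protocol 9.4 (Adverse Events) describes the AEs to be analysed as those with onset in the double-blind period, and explains this in a parenthesis: "i.e., TEAEs, and AEs that have worsened since baseline [Day 1]) will be included in the analysis". SAP Appendix 2 says: "There have been no changes to protocol-planned analyses".

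Two other places bear on the point. Protocol 8.8.1 has AEs reported from signed consent, about 8 weeks before Day 1. Protocol Appendix 4 defines an AE to include aggravation of the baseline condition in severity or frequency.

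**The concern.** The protocol names worsening since Day 1 as something the AE analysis must include. The SAP has no criterion that implements it, and does not list the difference as a change. Safety and tolerability against placebo is a secondary objective. The reactions that Protocol 4.2 attributes to JNJ-40411813 (dizziness, vertigo, abnormal coordination, fatigue, with somnolence also reported) overlap with those that Protocol 2.2.3 and 2.2.4 give for brivaracetam and levetiracetam. Worsening of a complaint already on file is therefore a plausible form of drug effect.

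Elsewhere the SAP does compare post-baseline with baseline findings: laboratory tests, vital signs and ECG each have such a rule (5.6.2.1 to 5.6.2.3). AEs have none.

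**Working it through.** The plan states no figure to reproduce. The check is to follow each kind of AE record through the two rules.

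1. **Dizziness that starts after Day 1.** Its onset lies in the window, so both documents count it.
2. **Dizziness that predates consent, held as a baseline condition, and first recorded as an AE when it worsens on treatment.** Protocol Appendix 4 makes the aggravation an AE. Its record starts on treatment, so both documents count it.
3. **Dizziness first recorded as an AE between consent and Day 1, ongoing at first dose, then worse on treatment, with the worsening kept on the same record.** Protocol 9.4 names it as worsened since Day 1. Under SAP 5.6.2 its onset precedes the double-blind start date, so it is assigned to no treatment phase and is not treatment-emergent. The partial-date rule does not rescue it, because the onset is known to be pre-dose.
4. **An AE that starts on placebo and worsens after the switch to open-label drug, on the same record.** By onset date it stays in the double-blind phase, and the worsening is not counted in the open-label phase.

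Case 3 is the gap. It can arise because AE records open at consent. The protocol also expects some AEs in this interval: section 6.5 allows a one-time adjustment of a background antiepileptic drug, during baseline as well as treatment, for AEs attributed to it.

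Outputs for case 3: the summary tables are limited to treatment-emergent events, so it is in none of them. If it becomes serious or leads to discontinuation, it appears in a listing. Otherwise it is in no AE output.

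Scale per affected participant, using the planned arm sizes in Protocol 6.3 (change in incidence = 100 / arm size):

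- Active arm, either cohort: 100 / 40 = 2.5 percentage points.
- Placebo, Cohort 1: 100 / 20 = 5 points.
- Placebo, Cohort 2: 100 / 10 = 10 points.

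How many participants fall in case 3 cannot be worked out. Neither document gives a rate of new AEs in the baseline period that persist to Day 1, nor a rate of worsening among them.

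**The case against.** The best defence rests on the protocol's own syntax. The parenthesis in 9.4 follows the words about onset in the double-blind period and begins with an i.e., so a worsened AE can be read as one kind of AE with onset in that period. With the Appendix 4 definition, a worsening on treatment is then itself an AE occurring on treatment, and the SAP's opening definition would cover it. This has force: it is why case 2 is not a problem. It does not settle case 3. Even on this reading, something must give the worsened event an on-treatment onset. The SAP contains no such rule, and neither document says that a severity increase on an existing AE opens a new record with a new start date.

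That convention may be in the eCRF completion guidelines, which the protocol promises under Data Quality Assurance but which are not part of these documents. If they require a new record, the gap closes in practice. That has to be confirmed.

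Some losses are also softened. Serious and discontinuation events are listed. SAP 5.6.1 lists all dose adjustments with reasons, so a worsening that leads to one leaves a trace there.

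A reader might go further in four ways that the documents do not support:

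- That any background-drug dizziness or sleepiness that worsens is lost. Most complaints from long-standing treatment would predate consent and belong to case 2.
- That the number affected can be gauged from frequencies such as the brivaracetam entry, "Very common: may affect more than 1 in 10 people somnolence dizziness". Those are general adverse-reaction frequencies. They do not measure new AEs that start during a baseline period on unchanged drugs and persist to Day 1, still less those that then worsen.
- That the loss falls mainly on the active arm. This is plausible pharmacologically, but no passage gives its direction or size.
- That the open-label rule breaches the protocol. The worsening wording is tied to Day 1 and the double-blind period, and Protocol 10.9.4 only refers back to 9.4.

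**Conclusion.** The concern holds for one defined group: AEs first recorded between consent and first dose, ongoing at Day 1, whose worsening on treatment stays on the same record. Protocol 9.4 names worsened AEs for analysis. SAP 5.6.2 as written leaves these out of all its AE summary tables and, unless they are serious or lead to discontinuation, out of its AE listings. Appendix 2 does not declare this.

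The number affected is unknown and may be small. Because the arms are small, each affected participant matters: 2.5, 5 or 10 points of incidence in arms of 40, 20 or 10. The conclusion assumes that the eCRF does not already force a new record when severity rises; if it does, what remains is a wording mismatch. The open-label analogue is worth covering for consistency, but it is not a protocol departure.

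**What to change.** In SAP 5.6.2, add that an AE with onset before first dose which increases in severity or becomes serious between first dose and last dose plus 5 days is also treatment-emergent, dated from the worsening. As a sensible extension, apply the same rule to AEs ongoing at open-label start, so that worsening after the switch is counted in the open-label phase.

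Confirm that the eCRF completion guidelines have a severity increase recorded with its own date, since without that date the rule cannot be programmed; add the instruction if it is missing. If the team prefers to keep the onset-only rule, state the departure from Protocol 9.4 in SAP Appendix 2.

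The cost is one or two sentences in the SAP, a small change to the AE derivation and, if needed, one line in the eCRF guidelines. Some additional AEs may be counted. No other analysis changes.

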Participants are encouraged to complete at least the first 4 weeks of treatment when there are no safety concerns. Participants who have exceeded their pre-randomization monthly seizure count at Week 4, or within any 4-week interval after Week 4 ("4-week sliding window approach") up to Week 12, will have the option to discontinue the study drug for lack of efficacy and to perform the end of study/early withdrawal visit, to continue double blind treatment, or to enter the OLE period. Participants who have not exceeded the pre-randomization seizure count will continue the double-blind treatment period through Week 12 and will have the option to perform the end of study visit or to enter the OLE period.

Procedures performed in the OLE period are described in Section 10.

Participants will visit the study center according to the schedule in the Schedule of Activities (SoA).

After at least 55 patients in Cohort 1 and after at least 45 patients in Cohort 2 have completed at least 4 weeks of treatment, an interim unblinded review of all cumulative safety, PK and efficacy data of JNJ-40411813 available to that date will be performed to decide on whether there should be any addition or modification to the dose(s) in the following cohorts and subsequent clinical studies. If the results of the review are inconclusive with respect to the assessment of efficacy, a second interim review of the same cohort may be done after the last participant has completed the 12-week visit.

See Figure 1 for the study flow diagram.

The study assessments will be completed as described in the SoA in Section 1.2.

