1.1. Objectives and Endpoints

Double-blind Treatment Phase

Objectives	Endpoints
Primary	
The primary objective of this study is to evaluate the efficacy of up to 3 dose levels of adjunctive JNJ-40411813 compared to placebo based on the time to baseline monthly seizure count in participants with focal onset seizures who are receiving levetiracetam or brivaracetam and up to 3 other anti-epileptic drugs (AEDs).	Time to baseline monthly seizure count is defined, for each patient, as the number of days until the patient experienced the number of seizures equal to baseline monthly seizure count, up to the end of the 12-week double-blind treatment period.
Secondary	
To evaluate the overall safety and tolerability of adjunctive JNJ-40411813 compared to placebo in participants with focal onset seizures who are receiving levetiracetam or brivaracetam and up to 3 other AEDs.	Adverse events, significant changes in vital signs, ECG, CSSRS and safety laboratory results.
To evaluate the efficacy of up to 3 dose levels of adjunctive JNJ-40411813 compared to placebo based on percent reduction in the double-blind monthly seizure count, relative to the pre-randomization monthly seizure count, in participants with focal onset seizures.	Percent reduction in the double-blind monthly seizure count is defined as the double-blind monthly seizure count minus the baseline monthly seizure count, divided by the baseline monthly seizure count.
To evaluate the efficacy of JNJ-40411813 over the double-blind period using percent participants with seizure freedom and percent responders (>50% seizure rate reduction).	The proportion of participants with no seizures during the double-blind period, and the proportion with a greater than 50% reduction in monthly seizure count relative to baseline monthly seizure count.
To evaluate the pharmacokinetics (PK) of JNJ-40411813 and selected metabolites and levetiracetam or brivaracetam in participants	Plasma concentrations of JNJ-40411813 and levetiracetam or brivaracetam and metabolites

CONFIDENTIAL – FOIA Exemptions Apply in U.S.

Objectives	Endpoints
with focal onset seizures who are receiving levetiracetam or brivaracetam and up to 3 other AEDs.	at baseline (Day 1) and on study weeks 4, 8, and 12
Exploratory	

Open-Label Extension Phase

Objectives	Endpoints
Primary	

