Participants who meet study entry criteria at the end of the prospective pretreatment baseline period will be randomized to JNJ-40411813 or placebo, CCI. The dosage(s) of concomitant AEDs should not be increased, and new concomitant AEDs should not be added to the treatment regimen. Central randomization will be implemented in this study. Participants will be randomly assigned to one of two treatment groups (JNJ-40411813 or Placebo) based on computer-generated randomization schedules prepared before the study by, or under the supervision of the sponsor. The randomization will be balanced by using randomly permuted blocks stratified by the prescribed baseline

Dosages of JNJ-40411813 in the first cohort will be CCI or placebo for or placebo for . Dosages of JNJ-40411813 in Cohort 2 will and Co be or placebo for or placebo for 7 days, dose increase or placebo on day 8) and . In the following for cohorts, the dose of JNJ-40411813 will be determined based on an ongoing assessment of tolerability and safety results from the previous cohort. The highest dose in following cohorts will for . The highest dose selected to be administered by induced participants will be expected not to exceed the 95th percentile of the plasma Cmax for JNJ-40411813, based on a population PK and/or PBPK model, after repeated administration of The minimum dose that might be considered in successive cohorts will be

Participants are encouraged to complete at least the first 4 weeks of treatment when there are no safety concerns. Participants who have exceeded their pre-randomization monthly seizure count at Week 4, or within any 4-week interval after Week 4 ("4-week sliding window approach") up to Week 12, will have the option to discontinue the study drug for lack of efficacy and to perform the end of study/early withdrawal visit, to continue double blind treatment, or to enter the OLE period. Participants who have not exceeded the pre-randomization seizure count will continue the double-blind treatment period through Week 12 and will have the option to perform the end of study visit or to enter the OLE period.

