5.5.4. Analysis of Efficacy data in the Open-Label Extension

Efficacy assessments during the open-label extension phase include percent reduction in seizure frequency, the percent of participants with seizure freedom and the participant responder rate.

The percent reduction in the OLE monthly seizure count is defined as 100*(Baseline monthly seizure count - OLE monthly seizure count)/(Baseline monthly seizure count). The OLE monthly seizure count is defined as the total number of observable focal onset seizures occurring during the OLE period, multiplied by 28/X_{OLE}, where X_{OLE} is the number of days comprising the OLE.

Descriptive statistics (N, mean, SD, median, 25th percentile and 75th percentile) of the percent reduction in the OLE monthly seizure rate will be presented. The number and percentage of participants with seizure freedom at the end of the OLE period will be summarized. The number and percentage of participants who achieve a response during the OLE period will be presented.

The analyses will be performed for the FASOLE analysis set for the open-label phase.

Plots of the mean (±SE) percent reduction in seizure count over time spanning the double-blind and open-label phase will also be presented for the observed cases by the double-blind treatment group (in the form of an intervention sequence) pooled over and also treatment group by CCI If the nature of the outcome is nonparametric then box-plots for the percent reduction in seizure count will be presented instead.

5.6. (Other) Safety Analyses

All safety analyses will be based on the safety (SAF and SAFOLE) analysis sets based on actual intervention received, unless otherwise specified.

For all continuous safety variables, descriptive statistics by intervention group will include the N, mean, standard deviation, median, minimum, and maximum. Categorical variables will be summarized by intervention group using frequency counts and percentages.

Analysis of safety data in the open-label phase: All open-label safety data will be summarized by the intervention received in the double-blind phase (in the form of an intervention sequence), and overall.

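### Double-blind adverse events are summarised only as crude percentages, although optional efficacy exits from Week 4 can give the arms unequal time at risk

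*SAP*

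**What the plan says.** - **AE statistic.** SAP 5.6.2: for each event, "the number and percentage of participants who experience at least 1 occurrence of the given event will be summarized by intervention group". Protocol 9.4, Adverse Events: "the percentage of participants who experience at least one occurrence of the given event will be summarized by treatment group". SAP 5.6 sets the general rule: "Categorical variables will be summarized by intervention group using frequency counts and percentages". The tables listed in SAP 5.6.2 include no person-time rate, time to first event or fixed-window analysis.
- **Objective.** SAP 1.1 makes safety comparative: "To evaluate the overall safety and tolerability of adjunctive JNJ-40411813 compared to placebo".
- **Exit rule.** SAP 1.2 and Protocol 4.1 give the trigger as "Participants who have exceeded their pre-randomization monthly seizure count at Week 4, or within any 4-week interval after Week 4". These participants "will have the option to discontinue the study drug for lack of efficacy", or may choose "to continue double blind treatment, or to enter the OLE period". Before that, "Participants are encouraged to complete at least the first 4 weeks of treatment when there are no safety concerns".
- **Intent and status of exits.** Protocol 4.2 presents the time-to-event endpoint as a way to cut exposure to placebo or ineffective treatment. Protocol 7.2 counts an exit under the rule as completion of the double-blind period.
- **Counting window.** Under SAP 5.6.2, a double-blind AE is treatment-emergent up to 5 days after the last dose, or up to the start of open-label drug if that comes first.
- **Exposure.** SAP 5.6.1 summarises duration, duration categories, cumulative duration and dose days. Nothing links these to the AE tables.

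**The concern.** A crude percentage compares arms fairly only if they are observed for similar lengths of time. Here the design lets people leave because of their seizure count, which is the outcome the drug is meant to change. If the drug works, more of the placebo arm qualifies to leave. Placebo participants who leave have fewer days in which an AE can be counted, and AEs after a move to the OLE count in that phase. With identical AE rates per day, the drug arm would then show the higher percentage.

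At stake is the reading of tolerability. Protocol 4.2 ties dose choice for later cohorts to the incidence of serious AEs and of AEs leading to discontinuation, and cumulative safety data feed the interim reviews (Protocol 9.5, SAP 5.8).

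**Working it through.** **1. The plan's own figures.** Neither document states an AE rate, an exit rate or an expected exposure. The only calculable figures are the powers in SAP 3: 99% and 83% at 40:20 (50% and 30% further reduction) and 94% at 40:10 (50%), at one-sided 5%. The between-subject variability and overdispersion behind them are named but not given. With small assumed variances and a multiplicative effect, simulation gave 99.8-100%, 81-83% and 98-99%. No setting tried matched all three, so this neither reproduces the powers nor shows an error in them.

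**2. Inputs for the exposure check**
- From the documents: 15% placebo reduction and a further 50% or 30% on drug; eligibility of 3 to 100 seizures in each 4-week half of baseline and no gap over 21 days; the exit rule from Day 28; 84 days of treatment; a 5-day AE tail.
- Assumed: rates relative to baseline of 0.85 on placebo and 0.85 × 0.5 = 0.425 or 0.85 × 0.7 = 0.595 on drug; median baseline 10 seizures per 28 days with log-SD 0.9; response log-SD 0.3; daily variance/mean ratio 1.5; leavers go on the first qualifying day; the same AE hazard in both arms.

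**3. Eligible to exit before Day 84**
- 50% effect: 19% of JNJ, 66% of placebo. Head counts: 40 × 0.190 = 7.6 against 20 × 0.661 = 13.2 (40:20) or 10 × 0.661 = 6.6 (40:10).
- 30% effect: 39% of JNJ, 67% of placebo. Head counts: 40 × 0.391 = 15.6 against 20 × 0.666 = 13.3 or 10 × 0.666 = 6.7.

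**4. Crude AE percentage with no true difference.** Constant hazard h = -ln(1 - 0.20)/89 = 0.00251 per day, where 89 = 84 + 5. Crude percentage = mean of 1 - exp(-h × (days + 5)). The last column instead puts 75% of the cumulative hazard in the first 14 days.

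| Effect | Uptake of exit | Mean days JNJ / placebo | Crude % JNJ / placebo | Gap, constant hazard | Gap, early onset |
|---|---|---|---|---|---|
| 50% | 25% | 82.1 / 76.5 | 19.6 / 18.4 | 1.2 points | 0.4 |
| 50% | 50% | 80.4 / 68.7 | 19.2 / 16.7 | 2.5 | 0.7 |
| 50% | all | 76.7 / 53.6 | 18.4 / 13.5 | 4.9 | 1.4 |
| 30% | 25% | 80.0 / 76.3 | 19.2 / 18.4 | 0.8 | 0.2 |
| 30% | 50% | 76.2 / 68.7 | 18.3 / 16.7 | 1.6 | 0.4 |
| 30% | all | 67.9 / 53.5 | 16.6 / 13.5 | 3.1 | 0.9 |

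Hand check of the third row, using mean days: 1 - exp(-0.00251 × 81.7) = 18.5% and 1 - exp(-0.00251 × 58.6) = 13.7%. These sit slightly above the simulated values, as expected when a mean is put into a concave function.

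**5. Higher AE risk.** At 30% over 84 days, with full uptake and a 50% effect, rounded mean days give 1 - 0.7^(77/84) = 27.9% against 1 - 0.7^(54/84) = 20.5%, a gap of 7.4 points. Simulation gave 25-28% against 20%, so up to about 8 points.

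**6. Opposing force.** Take the 30% effect and assume 5% of placebo participants stop for AEs at Day 14.

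| JNJ stopping for AEs | Uptake of exit | Mean days JNJ / placebo |
|---|---|---|
| 10% | 25% | 73.5 / 73.2 |
| 20% | 25% | 66.9 / 73.2 |
| 20% | all | 57.1 / 51.6 |

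The exposure gap can vanish, reverse or persist.

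**7. Does the remedy work?** First events divided by participant-time to first event or end of window estimate h in each arm. Under constant hazard the ratio is 1.00 by construction, whatever the exit pattern.

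**The case against.** The strongest case against has four parts.

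- **Imprecision and direction.** The safety analysis is descriptive, with no test, and the arms are small. At 25% against 20%, the standard error of the difference is √(0.25 × 0.75/40 + 0.20 × 0.80/20) = 11 points at 40:20 and √(0.25 × 0.75/40 + 0.20 × 0.80/10) = 14 points at 40:10. Even the largest gap above is less than one standard error, and efficacy exits push against the drug, so they do not hide harm. This stands as a limit on weight. It does not make the crude percentage the better summary, and a systematic shift does not average out when cohorts are combined.
- **Timing.** The protocol expects dizziness-type events early: Section 2.3.1 introduces up-titration to reduce early-onset AEs. Most would fall in the four weeks that participants are encouraged to complete. This stands; for such events the gap is about 1.4 points or less at 20% risk.
- **Visibility.** SAP 5.6.1 would reveal unequal exposure, and the interim reviews have a separate charter and short SAP that are not available here. This stands in part: a duration table warns the reader but corrects no AE percentage.
- **AE dropout.** Stopping for AEs shortens drug exposure, and Protocol 7.1 foresees an unblinded review if such stops exceed 10% of participants. This stands, and it is a further reason not to read crude percentages alone.

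A reader might also extend the point to the OLE as a biased drug-placebo comparison. The documents do not support that: everyone in the OLE receives JNJ-40411813 (Protocol 10.6.3) and no hypothesis testing is planned there (Protocol 10.3, 10.9.2).

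**Conclusion.** The gap in the plan is real: the objective is comparative, exit may depend on seizure outcome, and no AE summary allows for time at risk. The consequence is conditional. If the drug works and eligible participants use the option, crude percentages can overstate AEs on drug. The extent depends on uptake, AE timing and variances, none of which the documents give; every exit, uptake and AE rate used above is assumed.

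Two stronger readings are tempting and not supported.

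- **That the exits will be mostly placebo.** Neither document says so. With 2:1 or 4:1 allocation, placebo clearly outnumbers JNJ among eligible participants in only one of the four scenarios (about 13 against 8, 40:20 with the 50% effect). What follows, if the drug works, is a higher proportion within the placebo arm, and that is all the mechanism needs.
- **That the safety comparison is biased, by several points.** Continuing double-blind is an allowed choice, and the larger gaps need full uptake on the first qualifying day and a constant hazard. The comparison can be biased, and AE dropout can cancel or reverse the shift.

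This is a reporting gap worth closing because closing it is cheap. It is not an error in a stated figure.

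**What to change.** In SAP 5.6.2, keep every planned table and add two for the double-blind phase:

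1. Exposure-adjusted incidence for the treatment-emergent AE overview and common terms: participants with a first event divided by participant-time to first event or to the end of the treatment-emergent window, whichever is earlier. The window ends as SAP 5.6.2 already defines it, including for participants who move into the OLE. Give the between-arm difference with a 95% CI.
2. A crude n (%) table limited to onset on Days 1-28, the period before exit under the rule opens.

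For the OLE, exposure-adjusted rates may be shown descriptively, without a between-arm CI.

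The cost is two extra tables from dates already collected. The downside is that the rates assume a roughly constant hazard, which is doubtful for early-onset events; the Day 1-28 table offsets this. No clinical rule changes.
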